3.3 Preclinical Evidence

Bernafon requires evidence of operational safety and medical effectiveness of the devices before testing them. This evidence includes the device-related performance data in accordance with IEC 118-7: Measurement of the maximum output level and the maximum gain. In addition to the performance testing, the hearing aids are verified with system tests to ensure that they function according to the requirements. The safety of the fitting software is demonstrated by a beta version that has passed through a complete systematic software test and ensures the functionality of the hearing aids in combination with the software. Please see chapter B3e of the IB.

3.4 Clinical Evidence to Date

A clinical literature evaluation is maintained and has been updated in 2017. The basic benefit of hearing aids does not change with newly released devices. They are designed to amplify sound. The benefit of hearing aids has been shown in various studies (Kochkin, 2011). The evaluation includes an analysis of adverse events for Bernafon products as well as competitor devices that is used as post market analysis of the devices. The same Mermaid 9 device in a different hardware style was released to the market in early 2017. To date, there have been no adverse events reported on the U.S Food and Drug (FDA) Manufacturer and User Facility Device Experience (MAUDE) website.

Studies have concluded that different hearing aid styles can have an influence on comfort, occlusion, and feature functionality (Winkler et al., 2016). However, they all still provide the benefit of amplification.

A risk assessment is performed for all new devices. The primary risk identified is the possibility of over amplification from excessive sound pressure levels (further described in sec. 3.7). This risk is mediated by printing a warning in the Instructions for Use for hearing aids with high sound pressure level output capability. Additionally, when this type of instrument is selected in the software, there is a message warning the HCP of the sound pressure capability. Overall, Bernafon AG has had no adverse event reported in the last 16 years including no required modifications or recalls of products.

3.5 Medical Device: Rationale for the intended purpose in study (pre-market MD)

The IMD will be used in accordance with current use of hearing devices. The intended purpose of the study is to compare the performance of the IMD with the RMD that is currently sold on the market. In order to make an effective comparison the test participants will wear the IMDs for approximately 2 weeks.

3.6 Explanation for choice of comparator

The comparison device will be the current equivalent Bernafon BTE style of hearing aid (RMD) that has been available on the market since early 2017. The test participants will be fit with these devices during the trial to be able to compare them to the IMD. The reason for using the RMD is to control for performance differences caused by the new ITE style. Using a different style should, in theory, not affect the performance of the device.

3.7 Risks / Benefits

The audiological and psychoacoustic investigations are conducted using volunteer test participants with sound pressure levels that will not endanger their residual hearing. The test participants will be advised of the type, content, extent, and possible risks of the test beforehand. As psychometric methods are involved in the data collection, the risk for the test participants is judged to be extremely minor. However, the following risks shall be addressed:

Risk of hearing loss to residual hearing at too high a level in audiological and psychoacoustic experiments: Due to the test design (use of noise level up to a maximum of 100 dB SPL) and the hardware limitations of the measuring equipment (maximum output of loud speaker) the maximum provided sound level is restricted. During audiometry (test of hearing loss with audiometer) a level of more than 100 dB SPL must be used for test subjects who are profoundly hard of hearing; however, test subjects with profound hearing loss are not part of the inclusion criteria for this study

Post-trial care is organized in a manner that allows the test participants to contact the sponsor site and arrange an appointment for any maintenance of the devices as needed.

A device risk analysis and risk assessment have been conducted for the new device according to EN ISO 14971. This describes the anticipated adverse device effects, residual risks associated with the investigational device and the procedures involved in its use. It also explains that the anticipated clinical benefit outweighs the potential risks. Please see the Risk Assessment for details.

3.8 Justification of choice of study population

The choice of study population was determined by the goal of the study. The intended purpose of the study is to compare current Bernafon device performance against the new device and not the overall effect of amplification. Therefore, only participants that are hearing impaired and experienced hearing aid users will be included. Bernafon has its own database of test subjects that are used for clinical trials. They are current hearing aid users that use the Bernafon clinic for adjustments to fittings and general maintenance of their hearing aids performed by the audiologists working at Bernafon. These test subjects do not consist of employees of Bernafon or family members of employees. The test subjects for the current study will be chosen from this internal subject database.

The comparison between devices shall be made with experienced hearing aid users. It is important to compare the performance of the devices and the subjective opinions of the intended users. Testing normal hearing participants would not contribute information to this study. Test participants must be able to sign and understand the consent form to be included in the study. For emergency situations, the following applies:

-The standard procedure is to recommend that a subject see the ENT with whom they have an established relationship. If a subject does not have an ENT then it is agreed with [name] (Inselspital, Bern) that, if necessary, subjects from the trial could be referred to him.

4. STUDY OBJECTIVES

4.1 Overall Objective

The purpose of this study is to evaluate whether the IMD provides a similar or better performance than the RMD. The study aims to provide a final validation and quality control of the IMD before it is released for sales.

4.2 Primary Objective

The primary objective is to assess the effect that microphone location has on the speech scores of the end users. The speech scores of the IMD will be compared to the RMD.

4.3 Secondary Objectives

A secondary objective is to determine if the performance of the IMD is as good as the RMD. The performance of the IMD will be validated using the RMD as the control. The performance of the IMD should not be inferior to the RMD. The performance will be measured for both the RMD and IMD using a standardized questionnaire.

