
Outcome(s):
	
Primary Endpoint: The primary objective is to assess the effect of microphone location on end users' speech scores. Two standardized speech tests will be used. The speech scores achieved with the IMD will be compared to those with the RMD.
 
Secondary Endpoint: A secondary objective is to determine if the overall performance of the IMD is as good as the RMD. The performance of the IMD will be validated using a standardized questionnaire with the RMD as the control. The performance of the IMD should not be inferior to the RMD.
 
Other/Safety Endpoint: The study aims to validate the overall implementation of the new chip with the ITE hardware. A product questionnaire will be used to report unexpected behavior from the IMD and find any new risk factors to ensure safety of the devices before they are released to the market.

Study design:
	
This is a controlled, open label, comparative clinical investigation conducted monocentric at the premises of Bernafon AG in Bern, Switzerland.

Inclusion / Exclusion criteria:
	
Inclusion Criteria:
 
 • All classifications of hearing loss (sensorineural, conductive, mixed) • If the hearing loss is conductive or mixed it must be approved for amplification by a physician • All shapes of hearing loss (flat, sloping, reverse slope, notch) • Severity ranging from mild to severe • German speaking • Current hearing aid users • Both genders • Ages 18 and older • Ability and willingness to sign the consent form 
Exclusion Criteria:
 
 • Contraindications for amplification • Active ear disease • Inability to follow the procedures of the study due to language problems, psychological disorders, dementia, or other cognitive problems of the participant • A reduced mobility making them unable to attend weekly study appointments • Uncooperative so that it is not possible to record a valid pure tone audiogram • A strongly reduced dexterity • Central hearing disorders • Bernafon employees • Family members of Bernafon employees

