
Study Schedule:
	
The first participants will begin in June 2018 and the final data collection appointments will occur in July 2018.

Investigator(s):
	
[name], Research Audiologist, Doctor of Audiology [name] [contact] [contact]

Study Centre(s):
	
The testing will be performed at a single site in Bern, Switzerland at the Bernafon AG headquarters.

Statistical Considerations:
	
The analysis and documentation will be performed by the statistician using the latest validated R version with R Studio as IDE. Appropriate data analysis will be performed with parametric and non-parametric tests on questionnaire outcomes, hearing threshold measures, and speech test scores.

GCP Statement:
	
This study will be conducted in compliance with the protocol, the current version of the Declaration of Helsinki, the ICH-GCP or ISO EN 14155 (as far as applicable) as well as all national legal and regulatory requirements.

ABBREVIATIONS

Provide a list of abbreviations used on the protocol - to be completed

AE	Adverse Event
BASEC	Business Administration System for Ethical Committees, (https://submissions.swissethics.ch/en/)
CA	Competent Authority (e.g. Swissmedic)
CEC	Competent Ethics Committee
CRF	Case Report Form
ClinO	Ordinance on Clinical Trials in Human Research (in German: KlinV, in French: OClin, in Italian: OSRUm)
eCRF	Electronic Case Report Form
CTCAE	Common terminology criteria for adverse events
DSUR	Development safety update report
GCP	Good Clinical Practice
IB	Investigator's Brochure
Ho	Null hypothesis
H1	Alternative hypothesis
HRA	Federal Act on Research involving Human Beings (in German: HFG, in French: LRH, in Italian: LRUm)
IMP	Investigational Medicinal Product
IIT	Investigator-initiated Trial
ISO	International Organisation for Standardisation
ITT	Intention to treat
MD	Medical Device
MedDO	Medical Device Ordinance (in German: MepV, in French: ODim)
PI	Principal Investigator
SDV	Source Data Verification
SOP	Standard Operating Procedure
SPC	Summary of product characteristics
SUSAR	Suspected Unexpected Serious Adverse Reaction
TMF	Trial Master File

STUDY SCHEDULE

Study Periods	Intervention Period		
	Screening/1	2	3
Day	0	10 +/- 7 days	20 +/- 5 days
Patient Information and Consent	x		
Demographics	x		
Medical/Hearing History	x		
In-/Exclusion Criteria	x		
Randomization		x	x
Otoscopy	x	x	x
Audiometry	x		
Ear Impressions	x		

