7.3 Assignment to study groups

For the field tests the allocation is single group; therefore, all the test subjects will be assigned to the same group. The initial field test will be with the RMD and the second with the IMD, as it will take time

to have the IMD made by the lab.

For the lab tests the assignment to the test condition order will be randomized by the statistician. The test condition order will be randomized using a latin square design. This will minimize bias created when one test condition is tested in the final or last position all the time.

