9.3 Procedures at each visit

9.3.1 Screening/First Visit

Screening visit, Day 0: The potential participants will be given the Patient Information and Informed Consent form. The trial will be explained including how many visits are expected as well as the type of testing that they will complete. They are given time during the appointment to decide whether to participate in the study. If they choose not to take part in the study they will not sign the consent form, and the appointment will finish. If they choose to join the trial they will sign and date the consent form. No trial activities will be performed before the consent form is signed and dated by the subject and the investigator. Subjects will receive a copy of the signed consent form. A hearing history is then taken and otoscopy is performed. A hearing test is performed and inclusion/exclusion criteria will be determined. An ear impression is taken of each ear to create the IMD, and the RMD programmed to a first fit and adjusted using REM data in order to better match the electroacoustic output of the RMD and the IMD. They are given two questionnaires (APHAB and product) to complete at home regarding

the RMD. They are scheduled for the second visit. Any AEs are reported in the CRFs.

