9.3.2 Fitting/Second Visit

Fitting Visit, Day 10 +/-7: Otoscopy is performed, and the subjects are fitted with the IMD. Output of the IMD is measured, and the fitting adjusted, if necessary, to better match the electroacoustic output of the previously worn, RMD. They are randomized for the speech testing. Speech tests are made with the OLSA in three conditions: unaided, aided with RMD, and aided with IMD. The subjects return the RMD and held until the third appointment for further speech testing. The subjects return the completed questionnaires from the first visit and are given two more questionnaires (APHAB and product) to complete at home. They are given instructions about the IMD and an IFU with information about the IMD. They are scheduled for the third visit. Any AEs are reported in the CRFs.

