11.4 Planned Analyses

The analysis and documentation will be done by the statistician using R (version 3.4) a statistical software package. R “stats” package will be used for the confidence interval, non-inferiority, and Wilcoxon tests. Documentation of the analysis will be done with R Studio under R Markdown format.

Main outcome: speech reception threshold (SRT from OLSA and GÖSA)

SRTs from the OLSA test are measured during the second visit. OLSA data from a previous trial (BF001-1611) are used for the hypothesis definition, the non-inferiority margin, and the sample size calculation.

The rationale for the analysis is: paired t-tests usually test that the mean differences are zero. The non-inferiority test compares the difference to a non-zero quantity δ . The assumptions of the paired t-test are:

1. The data are continuous (not discrete).
2. The data, i.e., the differences for the matched-pairs, follow a normal probability distribution.
3. The sample of pairs is a simple random sample from its population. Everyone in the population has an equal probability of being selected in the sample.

SRTs from the GÖSA test are measured during the third visit. The GÖSA speech material is different than the OLSA, because it uses different vocabulary and presentation levels. The GÖSA contains short everyday sentences while the OLSA uses standardized, meaningless sentences. Collecting data from two different speech materials should help to generalize our findings. However, due to different test properties (Kollmeier et al., 2011), a separate analysis must be conducted with each test. As we don’t have reference data for the GÖSA test, we cannot compute a non-inferiority margin.. Therefore, the GÖSA analysis is planned as a secondary analysis and described in section 11.4.3.

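### The questionnaire (APHAB) cannot support the "not inferior" aim of section 4.3: device and period are confounded by the fixed order, and no margin or reference data are given

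*Protocol*

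**What the plan says.** **The aim.** Section 4.3 sets the secondary objective of finding out whether the IMD performs as well as the RMD on a standardized questionnaire, and adds: "The performance of the IMD should not be inferior to the RMD". The synopsis (Outcomes) carries the same aim: "The performance of the IMD will be validated using a standardized questionnaire with the RMD as the control". Section 9.2.2 names the instrument as the APHAB and says only that the two sets of results are compared.

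**The order.** Section 7.3 fixes the field sequence for all subjects: "The initial field test will be with the RMD and the second with the IMD". The reason given is the time needed to make the custom IMD. The questionnaires follow that sequence. At visit 1 (section 9.3.1), "They are given two questionnaires (APHAB and product) to complete at home regarding" the RMD. At visit 2 (section 9.3.2), when the IMD is fitted, "The subjects return the completed questionnaires from the first visit and are given two more questionnaires (APHAB and product) to complete at home". Randomisation covers the laboratory speech conditions only: "For the lab tests the assignment to the test condition order will be randomized by the statistician". Section 6.2.2 says the study is unblinded.

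**The analysis.** The only margin in the protocol is 1 dB SNR, for OLSA (section 11.1). Section 11.4 says no margin can be computed for GÖSA because there are no reference data, and makes GÖSA a secondary analysis. Section 11.4.3 covers OLSA and GÖSA and does not mention the questionnaires. The synopsis foresees "parametric and non-parametric tests on questionnaire outcomes", and in the same sentence on hearing thresholds and speech scores. Section 11.4 says the R package "will be used for the confidence interval, non-inferiority, and Wilcoxon tests", without assigning any of these to the APHAB.

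**The concern.** A non-inferiority conclusion needs a stated margin and a comparison in which the difference can be attributed to the device. The APHAB comparison has neither in this protocol.

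The fixed order is the more basic problem. A change in ratings between the first and second field periods could come from the device, from repeating the questionnaire, from novelty, or from expectation in subjects who know they have the new device. Any of these could hide a real deficit or create an apparent one. No later choice of test or margin can undo this, because no subject rates the IMD first.

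Section 4.1 describes the study as final validation before release for sales. An unsupported statement that users find the IMD no worse could enter that decision.

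**Working it through.** **1. The plan's own figure.** Section 11.2 uses n = (σ(z₁₋α + z₁₋β)/δ)² with σ = 1.6 dB, δ = 1 dB, α = 0.05 and power 0.80:

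n = (1.6 × (1.645 + 0.842)/1)² = 15.83, rounded up to 16.

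The stated 16 reproduces. It is for OLSA only; no size, SD or margin is given for the APHAB.

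**2. How the protocol treats its three comparative outcomes.**

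| Outcome | Order of devices | Margin | Stated aim |
|---|---|---|---|
| OLSA | randomised (Latin square) | 1 dB SNR | non-inferiority |
| GÖSA | randomised (Latin square) | none, for lack of reference data | exploratory, aided versus unaided |
| APHAB | fixed, RMD then IMD | none, no reference data given | not inferior |

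The outcome with the least protection keeps the stronger wording that GÖSA was not given. Section 6.2.1 recognises that order can bias speech scores and randomises for it; the questionnaires have no such protection.

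**3. Precision at the planned size.** The protocol gives no APHAB SD, so results are in units of the SD of the within-subject IMD–RMD difference. The half-width of the 95% confidence interval is t(0.975, n−1)/√n:

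- n = 16: 2.131/4 = 0.53 SD
- n = 20: 2.093/4.472 = 0.47 SD

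**4. If a non-significant paired test were the criterion (assumed).** For a true deficit of d SD, the test statistic follows a noncentral t with n−1 degrees of freedom and noncentrality d√n. The chance of missing the deficit is one minus the two-sided 5% power:

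| True deficit | n = 15 | n = 16 | n = 20 |
|---|---|---|---|
| 0.3 SD | 81% | 80% | 75% |
| 0.4 SD | 70% | 68% | 60% |
| 0.5 SD | 56% | 54% | 44% |

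The range 15 to 20 is the number of participants in the synopsis. The deficits are assumptions, shown as a range.

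**5. Would adding a margin be enough?** Suppose an APHAB margin were set, the true deficit equalled it, and a period effect of p SD favoured the second period. A one-sided 5% paired non-inferiority test then wrongly succeeds with the probability that a noncentral t with noncentrality p√n exceeds t(0.95, n−1):

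| Period effect | n = 16 | n = 20 |
|---|---|---|
| 0 | 5% | 5% |
| 0.2 SD | 19% | 22% |
| 0.3 SD | 31% | 36% |

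The period effect cannot be estimated from this design, so these are illustrations and not a predicted bias. They show that a margin alone does not repair the comparison.

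**The case against.** A reader might infer that the sponsor plans to take p > 0.05 on the APHAB as proof of non-inferiority. The documents do not support that. No section states such a rule. The synopsis phrase on parametric and non-parametric tests also covers speech scores, for which a non-inferiority test is planned, so it cannot mean difference tests only. Section 11.4 lists confidence-interval and non-inferiority methods and leaves open which applies to the questionnaires. The miss rates are therefore conditional on a criterion that the protocol does not give.

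It can also be said that the method and criterion for a secondary questionnaire are commonly left to the statistical analysis plan, which is not shown and might contain a margin. That is fair for the choice of test. It does not answer the confounding, which the visit schedule fixes, nor the inconsistency with GÖSA, which is within the protocol.

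The fixed order is disclosed and has a practical reason. Section 6.2.3 offers a partial mitigation: a fresh RMD fitting consistent with the IMD fitting, to reduce bias toward the previous device. Section 11.4.1 assumes that hearing is stable. Both are reasonable, but neither addresses novelty, expectation or repeat-rating effects in unblinded self-report.

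Finally, the only formal hypotheses are for SRT benefit, and the synopsis and section 6.1 call the study exploratory. This limits the consequence. It also argues for changing the wording of section 4.3, which does not match that label.

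**Conclusion.** The point holds in this form: the protocol sets a non-inferiority aim on the APHAB that its design cannot support. The confounding of device with period follows from the visit schedule and needs no assumption; its size is unknown. The absence of a margin and of reference data is a fact of this protocol and is inconsistent with how it treats GÖSA.

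The figures rest on assumptions: a paired t-test, roughly normal differences, and deficits expressed in SD units. If a non-significant test were the criterion, deficits of 0.3 to 0.5 SD would be missed about 80% to 54% of the time at n = 16 and 75% to 44% at n = 20. The protocol should not be described as planning that criterion.

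The primary OLSA analysis and the sample size are unaffected. The change should be made, because it governs what the trial may conclude on its secondary objective.

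**What to change.** In section 4.3 and the synopsis, replace the not-inferior wording for the questionnaire with a descriptive aim: to estimate the paired IMD–RMD difference in APHAB scores and report it with its 95% confidence interval. State that the fixed field order confounds device with period, and that no non-inferiority or equivalence conclusion will be drawn from the questionnaire. Keep the non-inferiority claim for OLSA, which has a margin and a randomised condition order.

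The field order need not change. The cost is wording plus one confidence interval, with no added visits, subjects or procedures. The sponsor gives up a secondary not-inferior statement, which is consistent with the exploratory label in the synopsis. Defining and justifying an APHAB margin instead would address only half of the problem, because the confounding would remain.
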